5.8.2 Efficacy Analyses

The hematologic response (CR, VGPR, PR, no change [NC], PD) rate will be tabulated and analyzed based on the Hematologic Response-Evaluable population and presented with a 2-sided 95% exact binomial confidence interval. In addition, the overall hematologic response rates up to the end of Cycle 3 and up to the end of Cycle 6 will also be tabulated and analyzed in a similar way.

Vital organ response rate will be tabulated and analyzed based on the Organ Response-Evaluable population. Organ-specific response rate will be tabulated and analyzed based on in the subgroup of the Organ Response-Evaluable population with amyloid involvement of the specific organ at baseline. Estimates of the organ response rate will be presented with 2-sided 95% exact binomial confidence intervals.

MLN9708**Study C16007 Statistical Analysis Plan**

Best hematologic response, time to hematologic response, time to best hematologic response, duration of hematologic response, time to hematologic PD, hematologic PFS, and OS will be presented in a by-patient listing. Vital organ response, organ-specific response, time to vital organ response, duration of vital organ response, time to organ PD, organ PFS, and OS will be presented in a by-patient listing.

Time to hematologic response, time to best hematologic response, duration of hematologic response, time to hematologic PD, hematologic PFS, and OS (1-year OS rate) will be analyzed using standard survival analysis techniques based on Kaplan-Meier estimates, if appropriate.

Raw values of serum M-protein, urine M-protein, serum free light chain (FLC), and the difference between amyloid-forming and nonamyloid-forming free light chain (dFLC), as well as the change from baseline, will be presented in by-patient listings. A waterfall plot will be generated to display the maximum change from baseline in dFLC.

QOL will be assessed for patients in the expansion cohorts only using the European Organisation for Research and Treatment of Cancer Quality of Life Questionnaire-Core 30 (EORTC-QLQ-C30, multiple myeloma module). Descriptive statistics will be presented for both the actual values and the changes from baseline in EORTC-QLQ-C30 assessment over time. EORTC-QLQ-C30 assessments will be analyzed to determine if hematologic response to therapy is accompanied by measurable improvement in QOL.

5.9 Pharmacokinetic, Pharmacodynamic, and Exploratory Analysis

5.9.1 Pharmacokinetic Analyses

The PK Analysis population will be used for the description of the PK profile and for the estimation of PK parameters.

PK evaluation will be based on concentrations of MLN2238, the complete hydrolysis product of MLN9708, in specimens collected at prespecified times before and after drug administration. Actual sample collection times will be used for the calculation of PK parameters. In the event that actual collection times are either unreliable or missing, scheduled collection times will be used. For ease of presentation, scheduled collection times will be used to present results in tables and figures. Both scheduled and actual collection times will be presented in listings.

Concentrations of MLN2238 that are below the limit of quantification (BLQ) will be treated as zero. Concentration data that are considered anomalous may be excluded from the concentration summaries and plots and will not be used in the calculation of PK parameters. Evidence or explanation will be provided to justify the exclusion of data.

When summarizing concentrations or PK parameters, a minimum of 2 values is required to show the mean and geometric mean, and at least 3 values are required to show the standard deviation and coefficient of variation (CV). Summary statistics will be reported only if the calculated mean value is greater than the lower limit of quantification (LLOQ) and at least 50% of the values are nonzero.

5.9.1.1 Plasma and Whole Blood Pharmacokinetic Profiles

Individual patient plasma and whole blood concentration data will be listed. Concentrations will be summarized (N, mean, standard deviation, CV, geometric mean, median, min, and max) according to dose cohort and dosing cycle and day. Population mean and individual plasma and whole blood concentration-time data will be plotted by dose cohort and dosing cycle and day.

5.9.1.2 Plasma and Whole Blood Pharmacokinetic Parameters

The following PK parameters will be calculated by noncompartmental methods, as data permit, from concentration-time data:

Parameter	Definition	Units
C_{max}	Observed maximum concentration	ng/mL
T_{max}	First time C_{max} is observed	hr
C_{trough}	Observed concentration at the end of a dosing interval	ng/mL
AUC_{tau}	Area under the concentration-time curve, time 0 to end of dosing interval, estimated using the linear-log trapezoidal method	hr*ng/mL
λ_{z}	Terminal disposition phase rate constant	1/hr
$t_{1/2}$	Terminal disposition phase half-life	hr
Rac	Accumulation ratio	unitless

Different PK parameters are to be estimated following dosing on Day 1 and Day 15. For some of the doses, concentration data is collected only on either Day 1 or on Day 15. PK parameters will be calculated accordingly. The PK parameters to be estimated for each day of dosing are as follows:

MLN9708
Study C16007 Statistical Analysis Plan

PK Parameter	Dosing Day	
	1	15
C_{\max}	X	X
T_{\max}	X	X
C_{trough}	X	X
AUC_{tau}	X tau = 168 hr	X tau = 168 hr
λ_{z}		X
$t_{1/2}$		X
Rac		X

Individual patient parameter data will be listed. PK parameters will be summarized (N, mean, standard deviation, CV, geometric mean [as appropriate], median, min, and max) according to dose cohort and dosing cycle and day.

5.9.2 Pharmacodynamic Analyses

The Pharmacodynamic Analysis population will be used for the description of the pharmacodynamic profile and for the estimation of pharmacodynamic parameters.

The pharmacodynamic measure that will be analyzed is whole blood 20S proteasome inhibition. The inhibition is defined as the postdose proteasome activity times divided by the baseline proteasome activity. If the baseline proteasome activity is missing or is BLQ for a patient, then no inhibition will be calculated for that patient. Individual and mean whole blood 20S proteasome inhibition data will be plotted over time, and summary tabulations will be presented.

Actual specimen collection times will be used for the calculation of pharmacodynamic parameters. In the event that actual collection times are either unreliable or missing, scheduled collection times will be used. For ease of presentation, scheduled collection times will be used to present results in tables and figures. Both scheduled and actual collection times will be presented in listings.

Proteasome activity measurements that are BLQ will be treated as zero. Proteasome activity measurements that are considered anomalous may be excluded from data summaries and plots and will not be used in the calculation of pharmacodynamic parameters. Evidence or explanations will be provided to justify the exclusion of data.

When summarizing proteasome inhibition or pharmacodynamic parameters, a minimum of 2 values is required to show the mean, and at least 3 values are required to show the standard deviation and CV. Summary statistics will be reported only if at least 50% of the values are nonzero.

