1.3.1 Pharmacokinetics and Pharmacodynamics

MLN9708 completely hydrolyzes to the boronic acid MLN2238 in aqueous solutions. MLN2238 is the only form of MLN9708 measurable in plasma or urine.

Based on preliminary clinical data from the first-in-human study of MLN9708 (C16001), following IV administration of MLN9708, MLN 2238 shows multi-exponential plasma disposition, characterized by a rapid initial disposition phase ($t_{1/2}$ of < 0.25 hours), 1 or more intermediate disposition phases, and a slow terminal disposition phase ($t_{1/2}$ of > 4 days). The Day 1 and Day 11 extrapolated immediate post-IV bolus plasma concentration of MLN2238 (C0) and AUC show proportional increases with increasing dose. There is accumulation of MLN2238 with multiple dosing; AUC_{tau} following the Day 11 dose of MLN9708 is an approximately 4-fold accumulation of MLN9708 by Day 11 on the biweekly schedule.

The pharmacodynamic effect being evaluated in the development of MLN9708 is red cell proteasome inhibition as measured by whole blood 20S proteasome activity. Based on preliminary clinical data from study C16001, following IV administration of MLN9708, maximum whole blood 20S proteasome inhibition occurs at the earliest sampled time points (0.8 or 0.25 hours) and increases with increasing dose over the dose range studied. Inhibition is short-lived (approximately 4 hours) following the Day 1 dose but is prolonged following the Day 11 dose.

Further details on these studies are provided in the IB.

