3.2 Secondary Endpoints

[figure not shown]
The secondary endpoints include:

- Single- (MTD cohort) and multiple-dose plasma PK after oral MLN9708
- Whole blood 20S proteasome activity profile and inhibition parameters of multiple-dose oral MLN9708
- Organ response and organ improvement according to standardized criteria
- Overall hematologic CR + VGPR + PR
- Time to organ or hematologic response, measured as the time from the first dose of MLN9708 to the date of first documentation of a confirmed organ or hematologic response, respectively
- Duration of organ or hematologic response, measured as the time from the date of first documentation of a confirmed organ or hematologic response to the date of confirmed organ or hematologic disease progression, respectively
- Time to organ and hematologic progression, measured as the time from the date of the first dose of MLN9708 to the date of first documented organ or hematologic disease progression
- Organ and hematologic disease PFS, defined as the time from the date of the first dose of MLN9708 to the date of confirmed organ or hematologic disease progression or death, respectively.

- One-year survival, defined as the patient survival probability at 1 year after the date of first dose of MLN9708

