8.1.7 Pharmacokinetics, Pharmacodynamics, and Exploratory Analyses

Pharmacokinetic Analysis

[figure not shown]
PK analysis will be based on concentrations of MLN2238, the complete hydrolysis product of MLN9708.

Individual and mean plasma and whole blood concentration data will be plotted over time. Summary tables will be presented for the plasma and whole blood concentration data. Plasma and whole blood PK parameters will be estimated using noncompartmental analysis methods. The PK parameters calculated for individual plasma MLN2238 concentration-time data and whole blood MLN2238 concentration-time data will include, but are not limited to: C_{max} , T_{max} , and AUC_{tau} . PK parameters will be summarized using descriptive statistics.

Pharmacodynamic Analysis

[figure not shown]
Individual and mean whole blood 20S proteasome inhibition data will be plotted over time. Summary tabulations will be presented for the whole blood 20S proteasome inhibition data. Pharmacodynamic parameters of whole blood 20S proteasome inhibition will be estimated using noncompartmental analysis methods. The pharmacodynamics parameters calculated for individual whole blood 20S proteasome inhibition-time data will include, but are not limited to: maximum inhibition (E_{max}) and time of occurrence of E_{max} (TE_{max}). Pharmacodynamic parameters will be summarized using descriptive statistics.

CCI

Tumor Biomarker Analysis

CCI

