06 NOV 2012

PPD

MLN9708
Study C16007 Statistical Analysis Plan

LIST OF ABBREVIATIONS AND DEFINITIONS OF TERMS

Abbreviation	Term
AE	adverse event
ALT	alanine aminotransferase
ANC	absolute neutrophil count
AST	aspartate aminotransferase
AUC	area under the concentration versus time curve
AUC _{tau}	area under the concentration-time curve, time 0 to end of dosing interval, estimated using the linear-log trapezoidal method
AUE	area under the effect versus time curve
BLQ	below limit of quantification
CL	clearance
C _{max}	maximum concentration
CSR	clinical study report
C _{trough}	predose concentration
CR	complete response
CRF	case report form
CV	coefficient of variation
CYP	cytochrome P ₄₅₀
dFLC	serum differential free light chain concentration; difference between amyloid forming and non amyloid forming FLC
DLT	dose-limiting toxicity
DNA	deoxyribonucleic acid
ECG	electrocardiogram
ECOG	Eastern Cooperative Oncology Group
EORTC-QLQ-C30	European Organisation for Research and Treatment of Cancer Quality of Life Questionnaire-Core 30
EOS	end of study
EOT	end of treatment visit
E _{max}	maximum observed inhibition value
FLC	free light chain
Ht	height
Hr	hour
INR	international normalized ratio
IV	intravenous; intravenously
λ _z	terminal disposition rate constant
LLOQ	lower limit of quantification
MedDRA	Medical Dictionary for Regulatory Activities
Millennium	Millennium Pharmaceuticals, Inc., and its affiliates
MLN2238	the complete hydrolysis product of MLN9708 to the boronic acid
MTD	maximum tolerated dose
NC	no change
NCI CTCAE	National Cancer Institute Common Terminology Criteria for Adverse Events
ORR	overall response rate
PD	progressive disease (disease progression)
PK	pharmacokinetic(s)

MLN9708
Study C16007 Statistical Analysis Plan

Abbreviation	Term
PR	partial response
PT	prothrombin time
PTT	partial thromboplastin time
QTc	rate-corrected QT interval (millisecond) of electrocardiograph
SAE	serious adverse event
SAP	statistical analysis plan
SD	stable disease
$t_{1/2}$	terminal disposition half-life
TE _{max}	time of occurrence of E _{max}
US	United States
VGPR	very good partial response
WBC	white blood cell
WHO	World Health Organization
Wt	weight

TABLE OF CONTENTS

1. INTRODUCTION	6
1.1 Study Design.....	6
1.2 Study Objectives.....	7
1.2.1 Primary Objective	7
1.2.2 Secondary Objectives	7
1.2.3 Exploratory Objectives	7
2. POPULATIONS FOR ANALYSIS	8
2.1 Safety Population and Enrolled Patients	8
2.2 DLT-Evaluable Population.....	8

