5.9.2.1 Pharmacodynamic Profiles

Individual patient proteasome activity data and proteasome inhibition data will be listed. Proteasome inhibition will be summarized (N, mean, standard deviation, CV, median, min, and max) according to dose cohort and dosing cycle and day. Population mean and individual proteasome inhibition-time data will be plotted by dose cohort and dosing cycle and day.

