5.9.2.2 Pharmacodynamic Parameters

The following pharmacodynamic parameters will be calculated by noncompartmental methods, as data permit, from proteasome inhibition-time:

Parameter	Definition	Units
E_{\max}	Observed maximum proteasome inhibition	%
TE_{\max}	First time E_{\max} is observed	hr
$AUE_{\tau_{\alpha}}$	Area under the inhibition-time curve from time 0 to end of dosing interval (0-168 hours) estimated using the linear trapezoidal rule	hr*%

Individual patient parameter data will be listed. Pharmacodynamic parameters will be summarized (N, mean, standard deviation, CV, median, min, and max) according to dose cohort and dosing cycle and day.

In addition to the noncompartmental PK and pharmacodynamic analyses described in Section 5.9.1 and Section 5.9.2, PK and pharmacodynamic data collected in this study may be used for population PK and PK/pharmacodynamic modeling purposes. These analyses will be reported separately, as they will use PK and/or pharmacodynamic data collected in other clinical studies.

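### The SAP defines 20S proteasome inhibition as postdose over baseline activity, which is activity remaining, so Emax, TEmax and AUEtau would be reversed if programmed as written

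*SAP*

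**What the plan says.** SAP 5.9.2 names whole blood 20S proteasome inhibition as the pharmacodynamic measure and gives its only definition: "The inhibition is defined as the postdose proteasome activity times divided by the baseline proteasome activity". The same section sets BLQ activity to zero and adds: "Summary statistics will be reported only if at least 50% of the values are nonzero".

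SAP 5.9.2.2 builds three parameters on the inhibition-time data:

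- Emax, in %: "Observed maximum proteasome inhibition".
- TEmax: the first time at which Emax is seen.
- AUEtau, in hr*%: the area over 0–168 h by the linear trapezoidal rule.

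The SAP abbreviation list describes Emax as the "maximum observed inhibition value", and protocol 8.1.7 describes it as "maximum inhibition". Protocol 1.3.1, reporting the earlier IV study, says that "maximum whole blood 20S proteasome inhibition occurs at the earliest sampled time points" and that inhibition increases with dose. Protocol 3.2 lists as a secondary endpoint: "Whole blood 20S proteasome activity profile and inhibition parameters of multiple-dose oral MLN9708".

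**The concern.** Dividing postdose by baseline activity gives 1 (100%) when the drug does nothing and 0 when the proteasome is fully inhibited. The scale therefore runs opposite to its name and to every other use of the word in the two documents. All three pharmacodynamic parameters inherit the reversal, as do the mean and individual plots. A reader of the tables would see the largest values where the drug did least.

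There is also a knock-on effect through two rules that are sensible in themselves. A BLQ activity is scored 0, so on the stated scale complete inhibition scores 0. The nonzero rule would then withhold a summary at time points where most patients are BLQ, which are the time points of greatest effect.

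**Working it through.** The documents give no numerical value for inhibition, Emax or AUEtau, so there is no stated figure to reproduce. The check is algebra plus illustration.

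**Inputs from the documents.** Ratio definition, BLQ rule and nonzero rule: SAP 5.9.2. Parameter definitions, % and hr*% units, 0–168 h interval and linear trapezoid: SAP 5.9.2.2. Sampling at predose, 0.5, 1, 2, 4, 6, 24 and 168 h, with ± 4 h on the last sample: protocol sampling table for Cycle 1.

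**Algebra.** Let R(t) = 100 × activity(t) / baseline (the SAP formula in %) and I(t) = 100 − R(t) (loss of activity).

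- Emax: max R = 100 − min I, so the stated formula selects the sample with the least inhibition, and TEmax is the time of that sample.
- Error in Emax: max R − max I = max R − (100 − min R) = max R + min R − 100. It depends on how far activity recovers (max R) and how deep the effect goes (min R).
- AUEtau: the trapezoid is linear, so AUE(R) + AUE(I) = 100 × interval length. At 168 h this is 100 × 168 = 16,800 hr*%. Because actual times are used, the constant is 100 × 164 = 16,400 to 100 × 172 = 17,200 across the sampling window.

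**Illustration with assumed activities** (% of baseline at 0, 0.5, 1, 2, 4, 6, 24, 168 h):

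- A, strong effect with recovery: 100, 40, 30, 35, 55, 70, 92, 98
- B, weak effect: 100, 85, 80, 82, 90, 94, 98, 100
- C, no recovery, already reduced at predose: 70, 35, 25, 30, 45, 50, 60, 70

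True AUE for A, from inhibition 0, 60, 70, 65, 45, 30, 8, 2: 15 + 32.5 + 67.5 + 110 + 75 + 342 + 720 = 1,362. B and C are worked the same way.

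| Profile | True Emax | SAP-formula Emax (postdose) | Error (points) | True AUE | SAP-formula AUE | Sum |
|---|---|---|---|---|---|---|
| A | 70% at 1 h | 98% at 168 h | 98 + 30 − 100 = +28 | 1,362 | 15,438 | 16,800 |
| B | 20% at 1 h | 100% at 168 h | 100 + 80 − 100 = +80 | 291.5 | 16,508.5 | 16,800 |
| C | 75% at 1 h | 70% at 168 h | 70 + 25 − 100 = −5 | 6,211.25 | 10,588.75 | 16,800 |

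The SAP formula ranks B above A on both parameters, although A has the stronger effect. In C the two Emax values are close, but TEmax is still wrong (168 h instead of 1 h).

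**Nonzero rule under the SAP formula,** counting BLQ as 0:

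- 2 of 3 patients BLQ leaves 1/3 = 33% nonzero, so the summary is suppressed.
- 3 of 6 leaves 50%, so it is reported.
- 4 of 6 leaves 2/6 = 33%, so it is suppressed.

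**The case against.** The strongest reply is that this is a slip of wording. The sentence is ungrammatical, with a stray *times*, so text has probably been lost, in drafting or in reading the PDF. It cannot be programmed word for word, and the neighbouring definitions make the intent plain. A programmer would notice *inhibition* near 100% in patients with no drug effect. That is a fair account of how the error arose. But the gap falls where a multiplier such as 100 would go. Restoring it changes the units and leaves the direction wrong. The subtraction would have to stand earlier, where the sentence is intact. SAP section 6, which lists departures from the protocol, does not mention the definition either.

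Other points stand in part:

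- **Consequences.** The SAP plans no formal tests, and the activity profile named in the same endpoint is unaffected. Correct values can be recovered: "Individual patient proteasome activity data and proteasome inhibition data will be listed".
- **The constant.** The 16,800 figure holds for an interval of exactly 168 h on the percent scale. The reflection holds whatever the constant.
- **The profiles.** They are invented and measure nothing in this trial. The algebra does not depend on them.
- **BLQ effect.** It is conditional, because the documents do not say whether BLQ samples are expected.
- **Scope.** Day 1 samples are taken only at the MTD, so patients at other doses may have no pre-drug activity value. That may narrow who is affected, but it is a separate question.
- **Negative values.** Activity above baseline gives negative inhibition under the corrected formula. How to report it is also separate and does not support the present wording.

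**Conclusion.** The concern holds. The SAP's only definition of a listed secondary pharmacodynamic endpoint points the wrong way and contradicts both documents' own use of the term. Followed literally, it reverses the meaning of Emax and TEmax and replaces AUEtau with 100 × interval length minus its true value, that is, 16,800 hr*% minus the true value at 168 h. The size of the Emax error varies with recovery and depth of effect: +28, +80 and −5 points in the three assumed profiles.

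This rests on the percent scale in SAP 5.9.2.2 and a complete profile. The MTD, DLT and response analyses are untouched, so it is a correction the sponsor should make but not a threat to the trial's main conclusions.

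**What to change.** Replace the defining sentence in SAP 5.9.2 with: percent inhibition = 100 × (1 − postdose activity / baseline activity). State that Emax, TEmax and AUEtau are derived from that quantity.

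Keep BLQ activity at zero; it then scores 100% inhibition. Leave the nonzero rule on the inhibition scale, where it no longer suppresses complete inhibition.

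The cost is one SAP sentence, with no new data and no change to the BLQ or reporting rules.

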5.9.2.1 Pharmacodynamic Profiles

Individual patient proteasome activity data and proteasome inhibition data will be listed. Proteasome inhibition will be summarized (N, mean, standard deviation, CV, median, min, and max) according to dose cohort and dosing cycle and day. Population mean and individual proteasome inhibition-time data will be plotted by dose cohort and dosing cycle and day.

5.9.2.2 Pharmacodynamic Parameters

The following pharmacodynamic parameters will be calculated by noncompartmental methods, as data permit, from proteasome inhibition-time:

Parameter	Definition	Units
E_{\max}	Observed maximum proteasome inhibition	%
TE_{\max}	First time E_{\max} is observed	hr
$AUE_{\tau_{\alpha}}$	Area under the inhibition-time curve from time 0 to end of dosing interval (0-168 hours) estimated using the linear trapezoidal rule	hr*%

Individual patient parameter data will be listed. Pharmacodynamic parameters will be summarized (N, mean, standard deviation, CV, median, min, and max) according to dose cohort and dosing cycle and day.

In addition to the noncompartmental PK and pharmacodynamic analyses described in Section 5.9.1 and Section 5.9.2, PK and pharmacodynamic data collected in this study may be used for population PK and PK/pharmacodynamic modeling purposes. These analyses will be reported separately, as they will use PK and/or pharmacodynamic data collected in other clinical studies.

